3 STUDY DESIGN SUMMARY

This study is a three-part, partially blinded, placebo controlled, combined single ascending dose (SAD) with food-effect, multiple ascending dose (MAD) study, and a single dose relative bioavailability (BA) study conducted in one study center in the United States.

Safety will be assessed throughout the study for all subjects. Safety assessments will include physical examinations, vital signs, serial ECGs, cardiac monitoring, adverse events (AEs), and clinical laboratory tests (including hematology, serum chemistry, coagulation, and urinalysis).

Part 1:

Part 1 is a SAD design with 6 planned dose levels. Additional cohorts may be enrolled if deemed appropriate by the Sponsor to repeat a dose level or study another dose level. Interim PK analyses and safety assessments will be performed for the dose escalation decisions and to select the dose level at which to assess the food-effect. The food-effect cohort is planned with two parallel groups, one fasting and the other fed.

Current duration and scheduling of safety and PK sampling assumes that the terminal half-life ($T_{1/2}$) will be approximately 7 days. The number and timing of PK sampling and safety assessments may be further revised based on evolving PK and safety information.

Subjects will be housed in the clinic from at least 24 hours prior (from Day -1), until 7 days after dosing (Day 8).

Subjects from Dose Level 1 will return to the clinic to have subsequent follow up safety (collection of AEs) and PK assessments on Days 10, 14, 17, 21, and 28.

Food-Effect: Based on exposure levels from the first 4 completed cohorts, the 100 mg dose was chosen for the food-effect cohort. In this food-effect cohort, there will be two parallel groups, one fasting and the other fed. The fed group will enroll at least 10 subjects and the fasted group will include data from 6 subjects who completed Cohort 4 and at least 3 additional subjects who will be enrolled in the fasted group. All subjects in the food-effect cohort will receive active drug of TBAJ-876, 100 mg.

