Note: PK sampling for making a decision on escalating to the next dose will be through the morning trough sample of Day 8, and a dose escalation meeting will take place around Day 15 when interim PK data is available from the bioanalytical lab. Therefore, the dose escalation meeting and decision will be based on PK through the morning of Day 8 and approximately 14 days of safety data, depending on the turnaround time of the bioanalysis. Subjects will continue to be monitored for PK and safety up to 10 weeks or longer after the dose. The duration of the follow-up period will be based on the analysis of interim PK data. Available subjects from Cohorts 4 and 5, and all subjects in Cohort 6 will be asked to return bi-weekly (+/- 2 days) up to 10 weeks or longer postdose. Subjects will complete the same procedures as required for Day 28 at each visit.

Interim PK analyses and safety assessments will be performed for the dose escalation decisions and to select the dose for the food-effect assessment, and to reconsider, if needed, the PK sampling time points as the study progresses. All samples will be sent for analysis on active treatment, and only the bioanalytical lab will be unblinded and will only run the analysis on active treatment subjects. Data from the analysis used for the escalation meetings will only include active treatment subjects and will be blinded by subject.

Dose escalation to the next cohort (i.e., dose level) or any changes to PK sampling and safety assessment timepoints will not take place until the Sponsor, in conjunction with the Principal Investigator and Dose Escalation Committee, has determined that adequate safety, tolerability and PK from the previous cohort have been demonstrated to permit proceeding to the next cohort.

Additional cohort, Cohort 7: Eight (8) subjects will be enrolled, 6 to receive active drug and 2 to receive placebo. Subjects will receive a single dose under fasted conditions. Subjects will receive 800 mg TBAJ-876 or matching dose of placebo for TBAJ-876 Oral Suspension.

Subjects will follow the procedures in the Schedule of Assessments (Table 15) with the following clarifications:

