### 3 ENDPOINTS

#### 3.1 Pharmacokinetic Endpoints

For Part 1 (single ascending dose including assessment of food effect), serial blood samples will be collected pre-dose and post-dose through 28 days to determine concentrations of TBAJ-876 and its metabolites (M2 and M3) in plasma. Additional samples were collected on Days 42, 56, and 70 for Cohorts 4, 5, and 6. For cohort 7, additional samples were only collected on Day 14. Noncompartmental pharmacokinetic parameters of  $AUC_{last}$ ,  $AUC_{inf}$ ,  $C_{max}$ ,  $T_{max}$ ,  $C_{last}$ ,  $T_{last}$ ,  $AUC_{Extrap\%}$ ,  $\lambda_z$ , and  $t_{1/2}$  will be calculated from plasma concentrations of TBAJ-876 (parent), M2 (metabolite), and M3 (metabolite);  $CL/F$  and  $V_z/F$  will be calculated for TBAJ-876 only.

For Part 2 (multiple ascending dose), serial blood samples will be collected pre-dose and post-dose through 24 hours on study days 1 and 14 to determine concentrations of TBAJ-876 and its metabolites (M2 and M3) in plasma. Predose trough plasma samples will be drawn daily Days 1 through 14.

For Part 2 on study day 1, noncompartmental pharmacokinetic parameters of  $AUC_{last}$ ,  $C_{max}$ ,  $T_{max}$ ,  $C_{last}$ ,  $T_{last}$ ,  $AUC_{tau}$ ,  $\lambda_z$ ,  $t_{1/2}$ , and  $C_{24}$  will be calculated from plasma concentrations of TBAJ-876 (parent), M2 (metabolite), and M3 (metabolite);  $CL/F$  and  $V_z/F$  may be calculated for TBAJ-876 if reasonable.

For Part 2 on study day 14, noncompartmental pharmacokinetic parameters of  $AUC_{tau}$ ,  $C_{max}$ ,  $T_{max}$ ,  $C_{min}$ ,  $C_{trough}$ ,  $C_{avg}$ ,  $C_{24}$ ,  $RAUC$ ,  $R_{C24}$ , and  $R_{Cmax}$  will be calculated from plasma concentrations of TBAJ-876 (parent), M2 (metabolite), and M3 (metabolite);  $CL_{ss}/F$  and  $V_z/F$  will be calculated for TBAJ-876 only. Parameters such as  $\lambda_z$ , and  $t_{1/2}$  may be calculated as reasonable.

For Part 3 (relative bioavailability [RBA] including assessment of food effect [FE]), serial blood samples will be collected pre-dose and post-dose through 14 days to determine concentrations of TBAJ-876 and its metabolites (M2 and M3) in plasma. Noncompartmental pharmacokinetic

QMD Ref: Worldwide-TMP-ST-006-4.0 Effective: 12Aug2019	Governing QMD: Worldwide-SOP-ST-001
Confidentiality Statement	

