This document is the property of Worldwide Clinical Trials Inc. and may not be duplicated, copied, altered or removed from company without prior approval from Worldwide Quality Assurance or in compliance with Worldwide Standard Operating Procedures.

Worldwide Clinical Trials Controlled Quality Management Document		
 WORLDWIDE CLINICAL TRIALS	Sponsor:	Global Alliance for TB Drug Development
	Protocol Number:	TBAJ-876-CL001
STATISTICAL ANALYSIS PLAN – PHASE 1		

parameters of  $AUC_{last}$ ,  $AUC_{inf}$ ,  $C_{max}$ ,  $T_{max}$ ,  $C_{last}$ ,  $T_{last}$ ,  $AUC_{Extrap\%}$ ,  $\lambda_z$ , and  $t_{1/2}$  will be calculated from plasma concentrations of TBAJ-876 (parent), M2 (metabolite), and M3 (metabolite); CL/F and  $V_z/F$  will be calculated for TBAJ-876 only.

Pharmacokinetic parameters will be summarized by cohort using descriptive statistics. Summary statistics will also be presented by gender within each cohort.

A power model approach will be used to assess of dose proportionality for Part 1 and Part 2.

For the assessment of the effect of food on TBAJ-876 and metabolites in Part 1, the 90% confidence intervals for geometric mean ratios, test-to-reference, of  $AUC_{0-72h}$ ,  $AUC_{0-14d}$ , and  $C_{max}$  will be determined as appropriate.

Achievement of steady state concentrations during the multiple doses of TBAJ-876 (Part 2) will be assessed using Tukey's multiple comparison test at predose on all dosing days (Days 2-14) for each dose level separately.

For Part 3, food effect will be assessed using an analysis of variance (ANOVA) model with food condition as the fixed effect. The relative bioavailability analysis for the two strengths of TBAJ-876 tablets will be assessed using an ANOVA model with the strength of tablet administered under fasting conditions as the fixed effect.

Additional pharmacokinetic parameters may be calculated if deemed appropriate.

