## 6.2.11 Concentration-Time Data

Blood Samples for PK analysis in plasma will be collected at:

Part 1 (SAD):

- Predose, and 0.5, 1, 2, 3, 4, 5, 6, 8, 10, 12, 16, 20, 24, 28, 32, 36, 40, 44, 48, 54, 60, 66, 72, 80, 88, 96, 120, 144, and 168 hours after dosing, then on Days 10, 14, 17, 21 and 28.

Additional samples will be drawn on Days 42, 56, and 70 for Cohorts 4, 5, and 6.

- For Cohort 7, PK samples will be collected at predose (0), and 0.5, 1, 2, 3, 4, 5, 6, 8, 10, 12, 16, 20, 24, 28, 32, 36, 40, 44, 48, 54, 60, 66, 72, 80, 88, 96, 120, 144, and 168 hours (Day 14) after dosing.

Part 1 (FE):

- Predose, and 0.5, 1, 2, 3, 4, 5, 6, 8, 10, 12, 16, 20, 24, 28, 32, 36, 40, 44, 48, 54, 60, 66, 72, 80, 88, 96, 120, 144, and 168 hours after dosing, then on Days 10, 14, 17, 21 and 28.

Part 2 (MAD):

- Day 1: Predose, and 0.5, 1, 2, 3, 4, 5, 6, 8, 10, 12, 16, 20, 24 (pre-dose sample for Day 2).

QMD Ref: Worldwide-TMP-ST-006-4.0 Effective: 12Aug2019	Governing QMD: Worldwide-SOP-ST-001
Confidentiality Statement	

This document is the property of Worldwide Clinical Trials Inc. and may not be duplicated, copied, altered or removed from company without prior approval from Worldwide Quality Assurance or in compliance with Worldwide Standard Operating Procedures.

Worldwide Clinical Trials Controlled Quality Management Document		
 WORLDWIDE CLINICAL TRIALS	Sponsor:	Global Alliance for TB Drug Development
	Protocol Number:	TBAJ-876-CL001
STATISTICAL ANALYSIS PLAN – PHASE 1		

- Day 14: 0.5, 1, 2, 3, 4, 5, 8, 12, 16, 20, 24, 28, 32, 36, 40, 44, 48, 54, 60, 66, 72, 80, 88, 96, 120, 144, and 168 hours after dosing and on Days 42, 63, 84, 105, and 126.
- Additional or fewer samples may be collected at times to be determined based on the results from previous cohorts. Predose trough concentrations will be collected daily from Days 2 through 13.

Part 3 (RBA and FE):

- Pre-dose, and 0.5, 1, 2, 3, 4, 5, 6, 8, 10, 12, 16, 20, 24, 28, 32, 36, 40, 44, 48, 54, 60, 66, 72, 80, 88, 96, 120, 144, and 168 hours after dosing, then on Days 10 (240 h) and 14 (336 h).

Concentration-time data will be tabulated by part, nominal time, analyte, cohort (group for Part 3), and study day (for Part 2) using descriptive statistics. For presentation of the individual data and summary statistics, concentrations below the limit of quantitation (BLQ) will be set to zero.

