### 6.2.12.1 Part 1 PK Parameters

The following PK parameters will be calculated for TBAJ-876, M2, and M3 for Part 1:

Parameter	Definition
C max	Maximum plasma concentration, determined directly from individual concentration-time data
T max	Time of the maximum plasma concentrations
C last	Last quantifiable plasma concentration determined directly from individual concentration-time data
T last	Time of last quantifiable plasma concentration
AUC last	Area under the plasma concentration-time curve from time-zero to the time of the last quantifiable concentration (C last ), as calculated by the linear trapezoidal method
AUC 0-24h	Area under the plasma concentration-time curve from time-zero to 24 h postdose, as calculated by the linear trapezoidal method
AUC 0-72h	Area under the plasma concentration-time curve from time-zero to 72 hours postdose, as calculated by the linear trapezoidal method
AUC inf	Area under the plasma concentration-time curve from the time of dosing extrapolated to infinity, calculated as:  AUC inf = AUC last + C last /λ z , where λ z is the apparent terminal elimination rate constant calculated by linear regression of the terminal linear portion of the log concentration versus time curve
AUC Extrap	The percentage of AUC inf based on extrapolation, calculated as:

QMD Ref: Worldwide-TMP-ST-006-4.0 Effective: 12Aug2019	Governing QMD: Worldwide-SOP-ST-001
Confidentiality Statement	

This document is the property of Worldwide Clinical Trials Inc. and may not be duplicated, copied, altered or removed from company without prior approval from Worldwide Quality Assurance or in compliance with Worldwide Standard Operating Procedures.

Worldwide Clinical Trials Controlled Quality Management Document					
 WORLDWIDE CLINICAL TRIALS	Sponsor:	Global Alliance for TB Drug Development			
Protocol Number: TBAJ-876-CL001					
STATISTICAL ANALYSIS PLAN – PHASE 1					

Parameter	Definition
	$(1 - \text{AUC}_{\text{last}}/\text{AUC}_{\text{inf}}) * 100$ (see additional criteria in Section 6.2.12.3)

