### Dose Proportionality (Parts 1 and 2):

The pharmacokinetic parameters for TBAJ-876, M2, and M3  $C_{max}$ ,  $AUC_{last}$ ,  $AUC_{0-24h}$ ,  $AUC_{0-72h}$  and  $AUC_{inf}$  (Part 1);  $C_{max}$  and  $AUC_{tau}$  (Part 2, Day 1); and  $C_{max}$  and  $AUC_{tau}$ , (Part 2, Day 14) will be compared across doses to assess dose proportionality (i.e., proportionality of a change in systemic exposure with a change in dose). Statistical analyses will be done using a power model (Smith, 2000) of the following general form,

$$\ln(PK) = \ln(\beta_0) + \beta_1 \cdot \ln(\text{Dose}) + \varepsilon,$$

Where

$PK$  is the pharmacokinetic parameter tested (e.g.  $C_{max}$  or  $AUC$ )

$\ln(\beta_0)$  is the y-intercept,

$\beta_1$  is the slope (a value of  $\beta_1 \approx 1$  indicates linearity), and

$\varepsilon$  is an error term

The estimate of  $\beta_1$  with the 90% CIs will be reported along with the associated p-value and the dose range for proportionality. Dose proportionality plots will be created as well.

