### Food Effect (Part 1):

Statistical comparison of the PK parameters of TBAJ-876, M2, and M3 exposure ( $C_{max}$ ,  $AUC_{0-24h}$ ,  $AUC_{0-72h}$   $AUC_{last}$ , and  $AUC_{inf}$ ) will be performed using an Analysis of Variance (ANOVA) model for a 2-way crossover design on the ln-transformed data with treatment as the

QMD Ref: Worldwide-TMP-ST-006-4.0 Effective: 12Aug2019	Governing QMD: Worldwide-SOP-ST-001
Confidentiality Statement	

This document is the property of Worldwide Clinical Trials Inc. and may not be duplicated, copied, altered or removed from company without prior approval from Worldwide Quality Assurance or in compliance with Worldwide Standard Operating Procedures.

Worldwide Clinical Trials Controlled Quality Management Document		
 WORLDWIDE CLINICAL TRIALS	Sponsor:	Global Alliance for TB Drug Development
	Protocol Number:	TBAJ-876-CL001
STATISTICAL ANALYSIS PLAN – PHASE 1		

fixed effects and subject as a random effect. Conclusions regarding the results of the statistical analysis of PK parameters across treatments will be based on the ratio of the geometric means expressed as a percent (100×Fed/Fasted) and the 90% confidence interval about the ratio. A lack of food effect will be demonstrated if the 90% confidence intervals are fully contained within the limits of 80.00% to 125.00%.

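### Part 1 dose-proportionality and food-effect analyses test AUClast although scheduled sampling ends at Day 14, 28 or 70 by cohort; the common-window AUC0-14d named in SAP 3.1 is never derived or analysed

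*SAP*

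**What the plan says.** **Sampling end.** SAP 6.2.11 gives the general Part 1 schedule and the food-effect schedule as serial samples to 168 hours "and 168 hours after dosing, then on Days 10, 14, 17, 21 and 28" (the excerpt includes the 168-hour sample). SAP 3.1 adds samples "on Days 42, 56, and 70 for Cohorts 4, 5, and 6. For cohort 7, additional samples were only collected on Day 14". Protocol Section 3 limits the late visits further: "Available subjects from Cohorts 4 and 5, and all subjects in Cohort 6 will be asked to return bi-weekly", so Day 70 data are not assured for everyone in Cohorts 4 and 5.

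**Food-effect arms.** The fasted arm pools 6 subjects from Cohort 4 with at least 3 new subjects (SAP 1 and 4). The fed arm is at least 10 new subjects, all on the Day 28 schedule.

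**Parameter.** SAP 6.2.12.1 defines AUClast as the area "from time-zero to the time of the last quantifiable concentration". The fixed-window areas it defines for Part 1 are AUC0-24h and AUC0-72h only.

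**Analyses.** In SAP 6.10, Cmax, AUClast, AUC0-24h, AUC0-72h and AUCinf "will be compared across doses to assess dose proportionality" in a power model. The same five go into the Part 1 food-effect ANOVA, where "A lack of food effect will be demonstrated if the 90% confidence intervals are fully contained within the limits of 80.00% to 125.00" percent.

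**Conflict.** SAP 3.1 has a different food-effect list. It begins "For the assessment of the effect of food on TBAJ-876 and metabolites in Part 1, the 90% confidence intervals for geometric mean ratios" and then names AUC0-72h, AUC0-14d and Cmax. AUC0-14d appears in neither 6.2.12.1 nor 6.10.

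**The concern.** A parameter with no common cut-off is compared across groups whose schedules end at different times. Cohort 7 (800 mg) stops earliest and its neighbour Cohort 6 (400 mg) runs longest, so the top dose step is the most exposed. In the food-effect comparison the mismatch sits inside the fasted arm: up to 6 of its 9 subjects can be followed to Day 70, while every fed subject stops at Day 28.

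With truly proportional PK, AUClast would rise too little from 400 to 800 mg and slightly too much from 50 to 100 mg. With no food effect, the fed/fasted ratio would sit below 1 inside a formal 80-125% rule. The Part 1 dose-proportionality plots listed in SAP 9 (Figures 14.4.26 to 14.4.28) cover Cmax, AUC0-24h and AUC0-72h, so no listed plot would show the AUClast step.

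Not affected: Cmax, AUC0-24h, AUC0-72h, and the Part 3 comparisons, where all three groups stop at Day 14.

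**Working it through.** **1. Confirm the schedules.** The listed times from predose to 168 h number 30. Adding Days 10, 14, 17, 21 and 28 gives 35 samples, or 140 mL at 4 mL each. Adding Day 14 alone gives 31 samples, or 124 mL. Both match Protocol 6.7.1 (35 for Cohorts 1-6, 31 for Cohort 7).

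**2. Inputs.** Half-life t = 7 days is the protocol's planning value (Section 3: "Current duration and scheduling of safety and PK sampling assumes that the terminal half-life" is approximately 7 days). By the day rule in SAP 6.2.5, dosing is Day 1, so Days 14, 28 and 70 are T = 13, 27 and 69 elapsed days. Assumed, because the documents do not give them: drug is quantifiable to the last scheduled visit; the share f of AUC lying in the terminal phase is 1 or 0.6; and, as an alternative, t = 14 days.

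**3. Fraction of AUCinf captured** = 1 - f × 2^(-T/t). At t = 7:

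| | Day 14 | Day 28 | Day 70 |
|---|---|---|---|
| f = 1 | 0.724 | 0.931 | 0.999 |
| f = 0.6 | 0.834 | 0.959 | 0.999 |

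**4. Dose steps when the truth is 2** = 2 × captured(upper) / captured(lower).
- 400 to 800 mg: 2 × 0.724/0.999 = 1.45 (f = 1); 2 × 0.834/0.999 = 1.67 (f = 0.6). At t = 14: 0.98 and 1.40.
- 50 to 100 mg: 2 × 0.999/0.931 = 2.15 (f = 1); 2.09 (f = 0.6).

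**5. Power-model slope bias** = least-squares slope of ln(captured) on ln(dose) over the seven doses.
- 10-800 mg at t = 7: -0.026 (f = 1) or -0.014 (f = 0.6). The largest size is 0.028 over t = 3.5 to 21 days, or 0.031 (at 14 days) if only half of Cohorts 4 and 5 return.
- 10-400 mg at t = 7: +0.025 or +0.015. The low value at 800 mg cancels this upward drift.

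**6. Fed/fasted ratio when the truth is 1**, with k of 9 fasted subjects followed to Day 70 = [captured(Day 28)/captured(Day 70)]^(k/9).

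| k | t = 7, f = 1 | t = 7, f = 0.6 | t = 14, f = 1 | t = 14, f = 0.6 |
|---|---|---|---|---|
| 6 | 0.954 | 0.973 | 0.83 | 0.90 |
| 3 | 0.977 | 0.986 | 0.91 | 0.95 |
| 0 | 1.00 | 1.00 | 1.00 | 1.00 |

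The ratio is also 1.00 if nothing is quantifiable after Day 28.

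**7. Whether AUCinf fills the gap.** SAP 6.2.12.4 drops AUCinf at 20% extrapolation or more. The limiting half-life is T / log2(f/0.2): 5.6, 11.6 and 29.7 days for Days 14, 28 and 70 at f = 1; 8.2, 17.0 and 43.5 days at f = 0.6. At 7 days, Cohort 7 extrapolates 28% (fails) or 16.6% (passes). Its removal is possible, not certain, and removal depends on the cohort's schedule.

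**8. Check of the remedy.** I applied the linear trapezoid to the SAP 6.2.11 times, ending at 216 and 312 h for Cohorts 1-6 and at 312 h only for Cohort 7, which has no Day 10 visit. At t = 7, f = 1 the area is overstated by 0.30% and 0.93%, so the 400-to-800 mg step is 2 × 1.0093/1.0030 = 2.01. Over t = 3.5 to 21 days (non-terminal part given an assumed 12 h half-life) the step stays within 2.00-2.03 and the slope bias within 0.002.

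**The case against.** The strongest reply is that the planned outputs barely move. SAP 6.10 reports a slope, not pairwise dose steps. A bias of at most 0.028 is smaller than the slope's 90% interval half-width, about 0.036 to 0.070 for 42 subjects at an assumed between-subject CV of 20 to 40%. For food effect with 10 against 9 subjects, a ratio of 0.954 to 0.973 instead of 1 lowers the chance of meeting the 80-125% rule only from about 52% to 47-50% at an assumed CV of 20%, and from 7.0% to 6.6-6.9% at 30%. The study is not formally powered. The larger figures need a longer half-life, and the documents give no quantitation limit, observed half-life or number of Cohort 4 returners. AUC0-24h and AUC0-72h already give common windows, Tlast is reported, and SAP 3.1 names AUC0-14d and permits additional parameters.

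Much of this stands, and it limits the severity. It does not remove the problem. The slope is stable only because two errors cancel, and cohort geometric means would still show a step at 800 mg that looks like saturating exposure. AUC0-72h holds only 1 - 2^(-3/7) = 26% of AUCinf at 7 days in a one-phase profile, so it does not replace a long window. Permission to add parameters neither defines AUC0-14d nor takes AUClast out of the tested list. Sections 3.1 and 6.10 also disagree whatever the half-life proves to be.

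**Conclusion.** The concern holds and should be fixed. As written, SAP 6.10 places a schedule-dependent exposure measure in a dose-proportionality model and inside a formal 80-125% rule, and it contradicts SAP 3.1. That much follows from the text alone.

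The size is conditional on quantifiable concentrations at the last visit, on the half-life, on the terminal share of AUC and on how many Cohort 4 subjects returned. At the protocol's own half-life the food-effect bias is small and can be zero, the overall slope bias is small, and the 400-to-800 mg distortion is large. All three are secondary PK results reported beside unaffected metrics, so this does not threaten the primary safety objective.

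**What to change.** - In SAP 6.2.12.1, define AUC0-14d as the area from time zero to the Day 14 sample, nominally 312 h under the SAP 6.2.5 day rule.
- In SAP 6.10, use AUC0-14d in place of AUClast in the Part 1 power model and the Part 1 food-effect ANOVA, alongside Cmax, AUC0-24h and AUC0-72h. This also aligns 6.10 with 3.1.
- Keep AUClast as a descriptive parameter only.
- Treat AUCinf as supportive and state how many subjects per cohort the 20% rule removes. Do not exclude Cohort 7 in advance.
- Add a sensitivity food-effect analysis with Cohort 4 truncated at Day 28, which covers more of the exposure than 14 days.
- Separately, reconcile the nominal times in SAP 6.2.11. Part 3 Days 10 and 14 are labelled 240 and 336 h, against 216 and 312 h by the day rule (9 × 24 and 13 × 24). The Cohort 7 list attaches Day 14 to its 168 h sample. State that the non-compartmental analysis uses actual times; the labels matter for half-life only if nominal times are used.

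The cost is SAP wording and one extra non-compartmental output per subject from samples already in the schedule. The one loss is that exposure after Day 14 is only described, not tested, in the comparison across all cohorts.
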